12.6 Assessment of Efficacy

All subjects who have received at least one cycle of treatment and have their disease re-evaluated will be evaluable for assessment of objective response using the criteria for response detailed in Section 9.

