
STATISTICAL CONSIDERATIONS
	
a) Definition of primary outcome/endpoint:
 
Objective response rate is the proportion of patients who achieve either a partial or complete response.
 
Complete response is defined as disappearance of all target lesions and normalization of serum tumor markers (AFP and beta-hCG) for at least 4 weeks. Any pathological lymph nodes (whether target or non-target) must have reduction in short axis to <10 mm. Complete Response must be confirmed four or more weeks after initial CR is observed.
 
In patients whose only evidence of disease is elevated serum tumor markers (AFP or beta-hCG), then values must fall below the upper limit of normal for the assay employed and remain at that level for at least 4 weeks.
 
Partial response is defined as at least a 30% decrease in the sum of the diameters of target lesions, taking as reference the baseline sum diameters. This should be present on at least 2 measurements 1 month

apart. The serum tumor markers (AFP and beta-hCG) should be stable or decreasing. Partial Response must be confirmed four or more weeks after initial PR is observed.

In patients whose only evidence of disease is elevated serum tumor markers (AFP or beta-hCG), then values must fall $\geq 90\%$ below baseline pretreatment levels for beta-hCG or 50% decrease below baseline pretreatment levels for AFP and persist for 6 weeks. If both tumor markers are elevated and one falls below 90% the other should fall at least below 50% of baseline pretreatment levels.

b) Definition of secondary outcomes/endpoints:

Progression-free survival (PFS) time is the time measured from the date of initiation of therapy until disease progression or death, whichever comes first. Patients alive and progression-free will be censored at their last follow-up.

Overall survival (OS) is the time measured from the date of initiation of therapy until death, regardless of cause. Patients alive at the time of data analysis will be censored at their last date of contact.

c) Analytic plan for primary objective:

The ORR and its 95% exact CI will be summarized for the total population and by cohort using the F distribution method (Collett 1991).

d) Analytic plan for secondary objectives:

- Both PFS and OS will be estimates using the methods of Kaplan and Meier for each cohort separately.

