9. CRITERIA FOR DISEASE EVALUATION

Patients will be assessed every cycle by physical examination for response for disease progression and by serum AFP and beta-hCG. Patients will have appropriate radiographic diagnostic procedures (CT scan of chest, abdomen and pelvis) for evaluation of measurable disease at baseline within 28 days of initiation of the study. Imaging can be repeated if required to evaluate the disease (i.e. no elevation of serum tumor markers) before cycle 3, 5 and then every 4 cycles thereafter, at completion of treatment or as clinically indicated. Patients with stable disease or partial or complete response will be eligible for continued therapy.

9.1 The Response Evaluation Criteria in Solid Tumors (RECIST 1.1) will be used as follows:

9.1.1 Measurable disease:

Lesions that can be accurately measured in at least one dimension with longest diameter ≥ 20 mm using conventional techniques or ≥ 10 mm with spiral CT scan.

9.1.2 Malignant lymph nodes:

To be considered pathologically enlarged and measurable, a lymph node must be

>15 mm in short axis when assessed by CT scan (CT scan slice thickness recommended to be no greater than 5 mm). At baseline and in follow-up, only the short axis will be measured and followed.

9.1.3 Non-measurable disease:

All other lesions (or sites of disease), including small lesions (longest diameter

<10 mm or pathological lymph nodes with ≥ 10 to <15 mm short axis), are considered non-measurable disease. Bone lesions, leptomeningeal disease, ascites, pleural/pericardial effusions, lymphangitis cutis/pulmonis, inflammatory breast disease, and abdominal masses (not confirmed and followed by CT or MRI), are considered non-measurable.

Note: Cystic lesions that meet the criteria for radiographically defined simple cysts should not be considered as malignant lesions (neither measurable nor non-measurable) since they are, by definition, simple cysts.

'Cystic lesions' thought to represent cystic metastases can be considered as measurable lesions, if they meet the definition of measurability described above. However, if non-cystic lesions are present in the same patient, these are preferred for selection as target lesions.

9.2 Methods for Evaluation of Measurable Disease:

All measurements should be taken and recorded in metric notation, using a ruler or calipers. All baseline evaluations should be performed within 28 days before the beginning of the treatment.

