12.2 Endpoints

12.2.1 Definition of Primary Endpoint

Objective response rate is the proportion of patients who achieve either a partial or complete response

Complete response is defined as disappearance of all target lesions and normalization of serum tumor markers (AFP and beta-hCG) for at least 4 weeks. Any pathological lymph nodes (whether target or non-target) must have reduction in short axis to <10 mm.

Complete Response must be confirmed four or more weeks after initial CR is observed. In patients whose only evidence of disease is elevated serum tumor markers (AFP or beta-hCG), then values must fall below the upper limit of normal for the assay employed and remain at that level for at least 4 weeks.

Partial response is defined as at least a 30% decrease in the sum of the diameters of target lesions, taking as reference the baseline sum diameters. This should be present on at least 2 measurements 1 month apart. The serum tumor markers (AFP and beta-hCG) should be stable or decreasing. Partial Response must be confirmed four or more weeks after initial PR is observed.

In patients whose only evidence of disease is elevated serum tumor markers (AFP or beta-hCG), then values must fall $\geq 90\%$ below baseline pretreatment levels for beta-hCG or 50% decrease below baseline pretreatment levels for AFP and persist for 6 weeks. If both tumor markers are elevated and one falls below 90% the other should fall at least below 50% of baseline pretreatment levels.

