12.3 Sample Size and Accrual

An optimal Simon two-stage design will be used for each cohort of patients to differentiate between the null hypothesis that the response rate P is $\leq 5\%$ ($P \leq 0.05$) and

the alternative hypothesis that the response rate is $\geq 20\%$ ($P \geq 0.20$). These values were chosen for both arms based on what is clinically relevant per the investigators' experiences. There is no available data at this time for CD30-negative/unknown patients as brentuximab vedotin has not been tested for such patients. Under this design, the probability of early termination under the null hypothesis is 0.599. This design yields a type I error rate, α (probability of concluding that the drug is not effective when it is actually effective) of 0.047 and a power of 0.801 (type II error rate 0.199) when the true response rate is $\geq 20\%$. In the first stage in each cohort, 10 patients will be enrolled. If there are no objective responses, then that cohort will terminate. If ≥ 1 response is observed, then an additional 19 patients will be enrolled in the second stage for a total sample size of 29 patients per cohort. If 3 or fewer responses are observed out of the 29 patients, then Brentuximab will be declared as not worthy of further study for that cohort. If ≥ 4 objective responses are achieved, then brentuximab vedotin will be deemed active in refractory/relapsed NSGCT and worthy of further study.

We estimate enrolling 2 patients/month for the CD30 negative cohort and 1 patient/month for the CD30 positive patients.

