12.4 Analysis Datasets

Population	Definition
Enrolled	This will comprise all subjects who meet the eligibility criteria and are registered onto the study.
Efficacy	The efficacy population comprises all patients who have received at least one dose of the study medication. This population will be used for efficacy analysis.
Safety	The safety population comprises all patients who have received at least one dose of the study medication. This set will be used for safety analysis.

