12.7 Data Analysis Plans

12.7.1 Analysis Plans for Primary Objective

The ORR and its 95% exact CI will be summarized by cohort using the F distribution method (Collett 1991). This endpoint may also be tabulated by covariates, such as sex, age, race, categorized weight, categorized disease burden at baseline, prior treatment, and performance status. The maximum percent reduction in the sum of the products of the largest diameters of the nodes or nodal masses being followed for response assessment will be graphically displayed. ORR by intensity and pattern of CD30 expression will be tabulated by cohort.

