12.8 Interim Analysis/Criteria for Stopping Study

Each cohort will be evaluated after 10 patients enroll on the study to that cohort. If no responses are seen then that cohort will be closed for lack of efficacy.

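### Section 12.6 does not say how its response-evaluable set relates to the Section 12.4 efficacy population, so the ORR denominator is open; using the 12.6 set would push a non-zero ORR upward

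*Combined protocol and SAP*

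**What the plan says.** All references are to the combined protocol and SAP.

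- **Section 12.4 (Analysis Datasets)** defines the efficacy population as everyone who received one dose or more, and adds: "This population will be used for efficacy analysis".
- **Section 12.6 (Assessment of Efficacy)** states: "All subjects who have received at least one cycle of treatment and have their disease re-evaluated will be evaluable for assessment of objective response". It refers to Section 9 for the response criteria.
- **Section 12.2.1** defines the primary endpoint: "Objective response rate is the proportion of patients who achieve either a partial or complete response". It does not say which patients.
- **Section 12.7.1** gives the primary analysis: "The ORR and its 95% exact CI will be summarized by cohort", by the F distribution method. It names no population, whereas Section 12.7.2 names the safety population for toxicity rates.
- **Synopsis, analytic plan for the primary objective**: "The ORR and its 95% exact CI will be summarized for the total population and by cohort". It names no analysis set either.
- **Sections 12.3 and 12.8** set the two-stage rule on enrolled patients: "In the first stage in each cohort, 10 patients will be enrolled" and "Each cohort will be evaluated after 10 patients enroll on the study to that cohort". A cohort stops with no response in 10, and the drug is called active with 4 or more responses in 29.

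**The concern.** The two sets are not the same. A patient who is dosed and then dies or is lost before any reassessment belongs to the 12.4 population but not to the 12.6 set. Nothing in the plan says how that patient counts in the ORR.

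Such a patient cannot be a responder. Complete and partial response both need a post-baseline measurement and a repeat at four weeks or later (Sections 9.5 and 9.7). Moving from the 12.4 to the 12.6 set therefore leaves the numerator alone and can only shrink the denominator. In a single-arm trial with ORR as primary endpoint, no control group offsets that shift. Two analysts could follow the plan in good faith and report different primary estimates, and the choice could be made after the data are seen.

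**Working it through.** **1. The plan's own design figures.** Inputs from Section 12.3: null rate 0.05, alternative 0.20, stage 1 n = 10 (stop if 0 responses), total n = 29 (active if 4 or more). With X1 the stage 1 responses and X2 the responses among the next 19:

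- Probability of early stopping under the null = 0.95^10 = 0.5987 (plan: 0.599).
- P(active | p) = sum over x = 1 to 10 of P(X1 = x) × P(X2 ≥ 4 − x).
- At p = 0.05 this is 0.0468 (plan: 0.047). At p = 0.20 it is 0.8011 (plan: 0.801).

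The design reproduces. Its rule counts responses among 10 and then 29 enrolled patients. Leaving unassessed patients out of a reported percentage does not alter that count.

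**2. Effect on the reported ORR.** Let d be the number of dosed patients in a cohort who are never reassessed. The documents give no value, so d is assumed. Take 29 dosed patients and x = 4 responders, the fewest that make a cohort positive.

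- ORR = 4/(29 − d). Relative rise = 29/(29 − d).
- Exact 95% limits with n = 29 − d: lower = 2.5% quantile of Beta(x, n − x + 1); upper = 97.5% quantile of Beta(x + 1, n − x). This is equivalent to the F distribution form.

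| d (assumed) | ORR | 95% exact CI | Relative rise |
|---|---|---|---|
| 0 | 4/29 = 13.8% | 3.9 to 31.7% | none |
| 1 | 4/28 = 14.3% | 4.0 to 32.7% | 3.6% |
| 2 | 4/27 = 14.8% | 4.2 to 33.7% | 7.4% |
| 3 | 4/26 = 15.4% | 4.4 to 34.9% | 11.5% |

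At d = 3 the ORR moves by 15.4 − 13.8 = 1.6 percentage points, against an interval 31.7 − 3.9 = 27.8 points wide.

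**3. A cohort stopped at stage 1 with no response.** The ORR stays at 0% and only the upper limit, 1 − 0.025^(1/n), moves: 30.8% for 0/10 and 33.6% for 0/9.

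**4. How many patients could be affected.** Section 9 says: "Patients will be assessed every cycle by physical examination for response for disease progression and by serum AFP and beta-hCG". Section 7.3 requires an examination and both markers 21 ± 7 days after the last dose, whatever the reason for stopping. Section 9.8 follows early discontinuers for progression. Section 9.5 counts a sustained marker rise or unequivocal non-target progression as progressive disease, so progression can be recorded before the first on-treatment CT. Patients assessed in any of these ways could count as re-evaluated and stay in the 12.6 set as non-responders. What remains is mainly patients who die or are lost within the first few weeks.

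**The case against.** The strongest reply is that the plan names one efficacy population. ORR is an efficacy endpoint, so Section 12.4 covers it on its face. Section 12.6 mentions no rate, denominator or exclusion and does not say only. It can be read as stating who can be given a response category. Because the drug is given on Day 1 of each cycle, one dose and one cycle arguably coincide, which leaves the reassessment condition as the only real difference. The shift is also small beside the width of the interval.

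Much of this stands. A reader might infer that the plan gives two contradictory denominators; the text does not support that, because 12.6 never calls its set a denominator. The reply does not close the gap, however. Section 12.6 is the more specific text on objective response, an evaluable set is easily taken as the denominator, and no sentence links the two sections.

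Two stronger readings also go too far:

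- **That the type I error is inflated.** If the 10 and 29 places were filled only with evaluable patients, the response rate in those places would be p/(1 − u), with u the share not reassessed. For a true rate of 5% among dosed patients, the type I error would be 0.055, 0.064 or 0.090 at u = 5%, 10% or 20%. This presumes that unassessed patients are replaced. The plan has no replacement rule, and Sections 12.3 and 12.8 count enrolled patients.
- **That many patients would drop out of the set.** Section 1.2 cites a median PFS of 4 weeks, and the first on-treatment CT comes after cycle 2, at about 6 weeks. Progression before that scan does not by itself make a patient unassessed, for the reasons in step 4 of the working.

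**Conclusion.** The concern holds as an unresolved link between Sections 12.4 and 12.6 that leaves the primary ORR denominator open. The direction of the effect is certain if the 12.6 set is used and at least one dosed patient is never reassessed: a non-zero ORR and both exact limits rise. The size is probably small and rests on an assumed number of such patients. It also depends on what counts as re-evaluated, which Section 12.6 settles only by pointing to Section 9. The conclusion that the go/no-go decision, alpha and power are untouched rests on applying Sections 12.3 and 12.8 literally. The point should be fixed because it concerns the primary estimate and the repair is cheap; it does not threaten the design.

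**What to change.** - **Section 12.7.1:** name the Section 12.4 efficacy population (all dosed patients in the cohort) as the denominator of the primary ORR and its exact interval. State that dosed patients without a post-baseline disease assessment count as non-responders.
- **Section 12.6:** label the evaluable set as a sensitivity analysis, reported with the number of non-evaluable patients and the reasons, by cohort.
- **Sections 12.3 and 12.8:** no change is needed for this point.

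The cost is two or three sentences. Sample size, stopping rule, alpha and power stay as they are. The downside is that the reported ORR may be slightly lower than on the evaluable set.

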12.7 Data Analysis Plans

12.7.1 Analysis Plans for Primary Objective

The ORR and its 95% exact CI will be summarized by cohort using the F distribution method (Collett 1991). This endpoint may also be tabulated by covariates, such as sex, age, race, categorized weight, categorized disease burden at baseline, prior treatment, and performance status. The maximum percent reduction in the sum of the products of the largest diameters of the nodes or nodal masses being followed for response assessment will be graphically displayed. ORR by intensity and pattern of CD30 expression will be tabulated by cohort.

12.7.2 Analysis Plans for Secondary Objectives

- Both PFS and OS will be estimates using the methods of Kaplan and Meier for each cohort separately.
- Toxicities will be summarized by cohort using frequencies and rates calculated as the proportion of patients in the safety population experiencing SAEs, and treatment delays, reductions, and discontinuations due to AEs, and SAEs. Two sets of tables will be generated: one for the overall toxicities and one for toxicities related to the study medication (possibly related, probably related and definitely related). Toxicities will be grouped by system using MedRA preferred terminology. Grade 1 to 4 will be reported individually and also as grade 3/4. Deaths will be reported individually.

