2.1.2 Secondary Objectives

- 1) To determine the progression free survival in patients with relapsed/refractory NSGCT treated with brentuximab vedotin.
- 2) To determine the overall survival of patients with relapsed/refractory NSGCT treated with brentuximab vedotin.
- 3) To determine the safety and tolerability of brentuximab vedotin in this patient population.

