5. TREATMENT PLAN

- Eligible patients will be divided into two cohorts, those who are CD30 positive and those who are CD30 negative/unknown. Both groups will be treated similarly and in parallel but analyzed separately.
- CD30 status may be unknown in the unlikely case of tumor-marker-only relapse or when a fresh tumor biopsy is not feasible, and archival tumor tissue is not obtainable

despite efforts to do so. These patients will be included in the CD30 negative cohort for analysis purposes, since statistically NSGCT are more likely to be CD30 negative.

The number of such patients with unknown CD30 status should not exceed 5 patients.

- Enrollment to the study does not have to wait for determination of CD30 status prior to treatment, unless in the situation where one arm is closed for enrollment or an interim assessment of response for the Simon stage I phase is needed. For example:
 - The first 10 patients can enroll on the study and start on therapy without waiting for CD30 status assessment. Prior to enrolling patient number 11, CD30 status need to be determined for all patients to make sure an interim assessment of response for the Simon stage I phase is not needed (i.e. one arm is at 10 patients).
 - If an arm has closed for lack of efficacy, CD30 status need to be assessed prior to starting therapy to make sure that patients belong to the open arm.
 - If both arms advance to the second stage of the Simon design then enrollment can again be pursued without waiting for CD30 status until one arm is closed to accrual.
- Eligible patients will be treated with brentuximab vedotin at 1.8 mg/kg IV every 3 weeks (maximum dose of 180 mg) indefinitely until disease progression, unacceptable toxicity, or study closure.
- Eligible patients with grade 2 peripheral neuropathy at enrollment will be treated with brentuximab vedotin at 1.2 mg/kg IV every 3 weeks (maximum dose of 180 mg) indefinitely until disease progression, unacceptable toxicity, or study closure.
- Response to treatment will be assessed clinically with history, physical exam and tumor markers measurement (BHCG and AFP) on day 1 of each cycle and with CT scans after cycle 2, 4, and every 4 cycles thereafter while receiving treatment.

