12. STATISTICAL METHODS

12.1 Study Design

This is an open label, single agent, multicenter, phase II study with 2 cohorts evaluating the efficacy of brentuximab vedotin in “CD30 positive” and “CD30 negative/unknown” relapsed/refractory NSGCT who are otherwise considered non-curable. Both cohorts will be treated similarly and in parallel but analyzed separately.

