12.5 Assessment of Safety

Toxicities will be assessed based on the Common Terminology Criteria for Adverse Events (CTCAE) version 4.0. The maximum grade of each toxicity will be recorded for each patient over the course of treatment (all cycles). Toxicities will be recorded up until 30 days after the last day of treatment. The incidence of treatment delays, dose reductions, and early discontinuations of treatment due to toxicity or patient choice, will also be recorded as a means of assessing the tolerability of treatment for each cohort.

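### Safety tables that stop at Grade 3/4 leave a fatal toxicity out of its own severe row, and no all-treated safety column is stated

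*Combined protocol and SAP*

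**What the plan says.** Section 12.5 (Assessment of Safety) sets the counting rule: "The maximum grade of each toxicity will be recorded for each patient over the course of treatment (all cycles". The same section assesses tolerability cohort by cohort.

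Section 12.7.2 sets the tables. The unit of summary is the cohort: "Toxicities will be summarized by cohort using frequencies and rates calculated as the proportion of patients in the safety population experiencing SAEs", followed by delays, reductions and discontinuations. There are two sets of tables, one for all toxicities and one for those related to the study drug. On grades: "Grade 1 to 4 will be reported individually and also as grade 3/4. Deaths will be reported individually". No Grade 5 column, no row for Grade 3 or higher and no column for all treated patients is named.

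Three other statements bear on pooling:

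- The safety objective in 2.1.2 is not split by cohort: "To determine the safety and tolerability of brentuximab vedotin in this patient population".
- The analysis set in 12.4 is not split either: "The safety population comprises all patients who have received at least one dose of the study medication".
- Section 12.1 says: "Both cohorts will be treated similarly and in parallel but analyzed separately".

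**The concern.** Two features of the tables make the severe-toxicity summary less useful than it could be at no extra cost.

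The first is the gap at the top of the grading scale. With one maximum grade per toxicity, a patient who dies of a toxicity is counted at neither Grade 3 nor Grade 4 for it. The combined severe row for that toxicity is then lower than it would have been had the patient survived the same event at Grade 4. This is foreseeable: sections 10.9.4, 10.9.8, 10.9.9 and 10.9.11 describe fatal outcomes with this drug for infections, hepatotoxicity, progressive multifocal leukoencephalopathy and severe skin reactions.

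The second is the missing overall estimate. The objective asks about the treated population, but the stated tables answer only for each cohort. A cohort may hold as few as 10 patients, too few to say much about any but the commonest toxicities.

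**Working it through.** **The plan's own figures.** Section 12.3 gives 10 patients in stage 1 and 29 in all per cohort, with closure on 0 responses in 10. The maximum total is 58 (synopsis). The chance of closing at stage 1 when the response rate is 5% is 0.95^10 = 0.5987, against the stated 0.599. The rejection probability is the sum over x1 = 1 to 10 of P(X1 = x1) × P(X2 ≥ 4 − x1), with X1 from 10 patients and X2 from 19. It gives 0.0468 at 5% and 0.8011 at 20%, against the stated 0.047 and 0.801. The design reproduces, so the possible cohort sizes are 10 and 29, and the possible totals are 20, 39 and 58.

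**How likely the uneven split is.** Let P and Q be the two cohorts' closing probabilities, with the cohorts independent. Exactly one closes with probability P(1 − Q) + Q(1 − P). The closing probability is 0.5987 at a true response rate of 5% and 0.8^10 = 0.1074 at 20%.

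- Both at 5%: 2 × 0.5987 × 0.4013 = 48%.
- One at 20%, one at 5%: 0.1074 × 0.4013 + 0.5987 × 0.8926 = 58%.
- Both at 20%: 2 × 0.1074 × 0.8926 = 19%.

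**The Grade 5 gap.** For one toxicity, let x be the patients with maximum Grade 3 or 4 and d those for whom it was fatal. The stated row shows x/n. Grade 3 or higher is (x + d)/n. The difference is d/n: one death is worth 1/29 = 3.4 points, or 1/10 = 10 points in a cohort closed at stage 1. The documents give no expected toxicity rate, so these counts are illustrative:

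| n | Grade 3/4 | Fatal | Row as planned | Grade 3 or higher |
|---|---|---|---|---|
| 29 | 6 | 1 | 20.7% | 24.1% |
| 29 | 6 | 2 | 20.7% | 27.6% |
| 29 | 0 | 1 | 0% | 3.4% |
| 10 | 3 | 1 | 30% | 40% |

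**The all-treated column.** The exact two-sided 95% upper limit for 0 events in n patients is 1 − 0.025^(1/n):

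| Patients | Upper limit |
|---|---|
| 10 (one cohort, closed at stage 1) | 30.8% |
| 29 (one full cohort) | 11.9% |
| 39 (pooled, one cohort closed) | 9.0% |
| 58 (pooled, both full) | 6.2% |

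For a toxicity seen in about 20.7% (again illustrative), the exact 95% interval is 8.0 to 39.7% for 6/29 and 11.2 to 33.4% for 12/58. The width falls from 31.7 to 22.2 points, about 30% narrower.

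**Whether dose argues against pooling.** Section 5 provides a second starting dose: "Eligible patients with grade 2 peripheral neuropathy at enrollment will be treated with brentuximab vedotin at 1.2 mg/kg IV every 3 weeks". It depends on neuropathy at enrolment, not on CD30 status, so it gives no reason to summarise safety by cohort alone.

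**The case against.** The strongest reply is that nothing is lost. Deaths are reported individually under 12.7.2. An event resulting in death is serious by the definition in 11.1.4, and footnote 7 to the study calendar makes any death within 30 days of stopping treatment an SAE whatever its cause. The proportion with SAEs is tabulated. A row labelled Grade 3/4 correctly counts Grades 3 and 4, and the plan promises no other severe rate. Reporting deaths individually might even mean giving them their own category beside Grades 1 to 4.

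Much of this stands. A reader might infer that fatal toxicity is concealed or vanishes from every rate; the documents do not support that. Nor do they name a headline severe-toxicity rate. What does not follow is that the per-toxicity rate is complete: neither a report of deaths nor an overall SAE proportion puts the patient back into the severe row for, say, hepatotoxicity.

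On pooling, the reply is that separate analysis is a stated choice, that no text forbids a total column, and that a reader can add two sets of counts. This also stands in part. Section 12.1 pairs similar treatment with separate analysis, so similar treatment alone cannot be read as a commitment to pool, and the absence of a pooled table is silence, not a prohibition. But an all-treated column beside the cohort columns respects the separate analysis. The synopsis already plans a total-population summary for the response rate; none is stated for safety. The main summary of a stated objective should not be left for readers to assemble.

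**Conclusion.** The point holds as a minor gap in the safety tables for a secondary objective. Each fatal toxicity leaves its Grade 3/4 row 3.4 points (n=29) or 10 points (n=10) below the rate of Grade 3 or higher. No stated table gives the safety estimate for all treated patients, which could lower a zero-event upper limit from 11.9% or 30.8% to 6.2%, or to about 9% if one cohort closes early.

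The first figure assumes that a fatal toxicity is graded above 4, which fits 12.7.2 setting deaths apart from Grades 1 to 4, and that the rows use the maximum grade from 12.5. If such a patient were also kept at the highest grade short of death, the gap would be nil, but the plan does not say so. The effect is confined to that toxicity's row; the patient's other toxicities keep their own grades. The limits are a yardstick for precision, since 12.7.2 plans no confidence intervals for toxicity. A pooled rate describes the mix of patients actually treated, at both starting doses.

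Two stronger readings fail. It is tempting to say that toxicity is estimated from half the patients; that is true only if both cohorts stop at the same stage, and otherwise the split is 10/39 (26%) and 29/39 (74%). It is also tempting to speak of one common regimen, but there are two starting doses, set by neuropathy. The primary response rule, its error rates and the stopping rule in 12.8, which uses responses alone, are unaffected.

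**What to change.** In section 12.7.2:

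- tabulate Grades 1 to 5 for each toxicity;
- report Grade 3 or higher, in place of or beside Grade 3/4, in both the overall and the drug-related tables;
- add an all-treated column beside the two cohort columns, keeping the separate cohort summaries and the individual reporting of deaths.

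The cost is table shells only, with no new data, visits or patients. Reported severe-toxicity rates may read slightly higher.
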